7.10 STUDY TREATMENT APPLICATION

Refer to [Section 0](#) for details.

7.11 POST-INJECTION EVALUATION AND INJECTION SITE REACTION ASSESSMENT

[figure not shown]
At each treatment visit, an injection site reaction assessment will be made for the current and previous injection sites. Injection site reaction assessments are recorded by the Investigator starting after the first injection is given. Subject will be observed at approximately 30 minutes post-injection or longer if necessary for injection site reaction as per CTCAE v5.0. Refer to [Sections 0](#) for more details.

7.12 PAIN SEVERITY ASSESSMENT

Tolerability of repeated subcutaneous administration of Leronlimab (PRO 140) is evaluated based on assessment of subject-perceived injection site pain using 11-point Numeric Pain Rating Scale.

Before each study treatment administration (T2 to T13, and at EOT), subjects will be asked to evaluate the pain intensity **over the past week** at the site of injection administration based on 11-point Numeric Rating Scale from 0 to 10. “0” meaning “no pain” and “10” meaning “worst possible pain”.

Figure 7-1: 11-Point Numeric Pain Rating Scale

7.13 FIBROSCAN

FibroScan ultrasound measures both liver fibrosis (scarring) and steatosis (fatty change). FibroScan steatosis (Controlled Attenuation Parameter (CAP)) score and fibrosis score will be evaluated for eligibility in this study.

7.14 LIVER MRI (MULTISCAN)

Liver MRI (MultiScan) is a non-invasive diagnostic technology for evaluating liver diseases using multiparametric MRI to non-invasively quantify liver tissue. Combining the information from multiple parametric maps provides a comprehensive analysis of liver tissue, which can be used to aid the diagnosis of liver disorders.

The Magnetic Resonance Imaging-derived Proton Density Fat Fraction (MRI-PDFF) is a novel imaging-based biomarker that allows fat mapping of the entire liver.

Corrected T1 (cT1) is also an MRI-based diagnostic imaging biomarker of the liver. cT1 is intended to be used as a proxy for inflammation and fibrosis.

In this study, Liver MRI will be performed to evaluate MRI-derived biomarkers such as PDFF and cT1 at SV and EOT/ET visits.

8 STATISTICAL ANALYSIS

This section presents general information about statistical considerations and concepts and a brief discussion on analysis methodology, as well as some data conventions. Detailed descriptions of the statistical analysis methods and data conventions that will be used in this study will be in a separate document; i.e., the Statistical Analysis Plan (SAP).

8.1 TREATMENT GROUPS

In Part 1 of the study, all eligible subjects will be randomized to receive PRO 140 as a 700mg subcutaneous injection or placebo weekly for up to 13 weeks.

In Part 2 of the study, all eligible subjects will receive PRO 140 as a 350 mg subcutaneous injection weekly for up to 13 weeks.

8.2 STUDY OUTCOME MEASURES

Primary Efficacy Outcome Measure:

- Change from baseline in hepatic fat fraction assessed by magnetic resonance imaging-derived proton density fat fraction (MRI-PDFF) at week 14

Secondary Efficacy Outcome Measures:

- Change from baseline in fibro-inflammatory activity as assessed by cT1 (corrected T1) assessed by multiparametric magnetic resonance imaging (MRI) of liver at week 14

Note: cT1 measured in milliseconds (ms) is a quantitative metric for assessing a composite of liver inflammation and fibrosis

- Change from baseline in liver fibrosis using FibroTest at week 14
- Change from baseline in hepatic inflammatory activity using FibroTest at week 14
- Change from baseline in serum pro-inflammatory biomarkers assessments
- Change from baseline in Gamma-glutamyltransferase (GGT) at week 14
- Change from baseline in CK-18 level at week 14
- Change from baseline in Leronlimab (PRO 140) PK assessments

Exploratory Outcome Measures:

- Change from baseline in Alanine transaminase (ALT) at week 14
- Change from baseline in Aspartate transaminase (AST) at week 14

- Change from baseline in total bilirubin at week 14
- Change from baseline in triglycerides at week 14
- Change from baseline in Low Density Lipoprotein (LDL) at week 14
- To explore Monocyte/T cell CCR5 biomarkers that may predict activity of leronlimab.

8.3 SAMPLE SIZE DETERMINATION AND RATIONALE

The sample size of 90 total subjects [60 subjects (30 subjects per arm) for the Randomized Phase and up to 30 subjects for the non-randomized, open-label phase] is selected on the basis of clinical judgment and not based on statistical power calculation. The number of subjects is deemed adequate to provide clinically meaningful descriptive results consistent with study objectives.

8.4 RANDOMIZATION

Subjects who are eligible to participate in the trial will be randomized to one of the treatment groups via IWRS (Interactive Web Based Randomization System) at the T1 Visit prior to IP administration. The randomization will be central and will use 1:1 ratio of Treatment groups A and B:

- PRO 140 700mg SC weekly injection (Group A)
- Placebo 0 mg SC weekly injection (Group B)

Note: Randomization is not applicable for the open-label, single-arm portion (Part 2) of the study.

8.5 BLINDING

All subjects, Investigators and their staff, and all Sponsor/CRO personnel involved in the management of the study will be blinded to treatment assignments.

The [REDACTED] Information Technology department will be unblinded to treatment. As noted above, the [REDACTED] Technology department is not otherwise involved with the study.

Treatment unblinding for the study will occur after all clinical data have been received, data inconsistencies have been resolved, and the database is locked, except for safety reasons on a case-by-case basis (i.e., emergency unblinding).

Note: Blinding is not applicable for the open-label, single-arm portion (Part 2) of the study.

8.6 INTERIM ANALYSIS

No interim analysis (IA) will be performed for efficacy.

8.7 GENERAL STATISTICAL CONSIDERATIONS

All collected study data will be presented in subject data listings. Statistical analyses will be performed using SAS® for Windows, version 9.4 or later. Descriptive statistics (n, mean, standard deviation, median, minimum and maximum) will be presented by treatment group for continuous variables. Frequencies and percentages will be presented by treatment group for categorical variables.

Analysis Populations

Intent-to-Treat Population

The **Intent-to-Treat (ITT) population** is defined as the set of subjects who have received at least one dose of study treatment (Leronlimab (PRO 140) or placebo) and have at least one post-baseline efficacy assessment. The ITT population will be used as the primary analysis population.

Per Protocol Population

The **Per Protocol (PP) population** is defined as the set of subjects who meet the ITT population requirements, were not associated with any major protocol violations and have at least 80% of compliance with study treatment. This population will be identified before the database lock.

The PP analysis of primary and secondary endpoints will be considered supportive.

Safety Population

The **Safety Population** will include all subjects who have received one dose of study treatment (Leronlimab (PRO 140) or placebo). This population will be used for the analysis of safety parameters.

Covariates

For efficacy analyses, the baseline values will be used as covariates in the analysis models. Other important prognostic factors will be specified in the SAP for the study.

Missing Data

All data will be used as observed, and no imputations will be made for any missing data point for early phase study.

8.8 ANALYSIS METHODS

A SAP will be developed and approved before the database is locked. The SAP will present the detailed statistical methodology to be used in analyzing the data from this trial. All inferential statistical analysis will be based on a two-sided test with a Type I error rate of 0.05.

All the efficacy analyses presented here will be conducted using both the ITT and PP populations. All safety analyses will be conducted using the Safety population. Continuous data summaries will

include number of observations, mean, standard deviation, median, and minimum and maximum values. Categorical data summaries will include frequency counts and percentages.

Subject Disposition

The disposition of all subjects who sign an ICF will be provided. The numbers of subjects screened, randomized, received treatment, completed, and discontinued during the study, as well as the reasons for all post-enrollment discontinuations will be listed and/or summarized by treatment group.

Demographic and Baseline Disease Characteristics

Demographics and baseline disease characteristics including medical history, prior and concomitant medications/therapies will be listed and/or summarized by treatment group using appropriate descriptive statistics.

Study Analyses

Efficacy Analysis

Analysis of the efficacy endpoints will be conducted according to below methods:

- If the Normality assumption is met, Analysis of Covariance (ANCOVA) or Mixed Model using the covariates in the model.
- If the Normality assumption is not met, a non-parametric method or a rank – ANCOVA analysis will be used.

Safety Analyses

Safety will be assessed by close monitoring and timely assessment of adverse events (AEs), laboratory parameters (blood tests, urinalysis), vital signs (blood pressure, heart rate), subject's medical condition (physical examination including weight). Tolerability of repeated subcutaneous administration of Leronlimab (PRO 140) as assessed by study participants (using 11-point Numeric Pain Rating Scale) and by investigator-evaluation of injection site reactions.

Adverse Events

Adverse events will be coded using the most recent version of Medical Dictionary for Regulatory Activities (MedDRA). Treatment Emergent AE's (TEAE) are defined as events with an onset on or after the first treatment. TEAEs will be summarized by treatment group, System Organ Class, and preferred term. The following TEAE summaries will be provided:

- by PT in descending order of frequency
- by SOC and PT
- by SOC, PT, and severity

- by SOC, PT, and relationship to study drug

Clinical Laboratory Data

All laboratory values will be listed. Laboratory measurements will also be summarized as continuous variable and presented by treatment group and time point.

Physical Examination

All physical examination findings will be listed and/or summarized.

Vital Signs

All vital sign findings will be listed and summarized.

Electrocardiograms (ECGs)

All ECG findings will be listed and summarized.

Tolerability

Pain severity assessment (using 11-point Numeric Pain Rating Scale) and injection site reactions will be listed and summarized.

9 ADVERSE EVENTS (DEFINITIONS AND REPORTING)

The Investigator is responsible for the detection and documentation of events meeting the criteria and definition of an AE or SAE, as provided in this protocol. During the study when there is a safety evaluation, the Investigator or site staff will be responsible for detecting, documenting and reporting AEs and SAEs as detailed in this Section of the protocol.

9.1 ADVERSE EVENT (AE)

An adverse event (AE) is defined as any unfavorable or unintended sign, symptom, or disease that occurs or is reported by the subject to have occurred, or a worsening of a pre-existing condition. An adverse event may or may not be related to the study treatment.

AEs will be elicited through direct questioning and subject reports. Any abnormalities in visit evaluations, physical examination findings or laboratory results that the investigator believes are clinically significant to the research subject and that occurred after initiation of the first study treatment will be reported as AEs. Abnormal findings that are NOT clinically significant should be not be recorded as an AE.

9.2 REPORTING AND FOLLOW-UP OF ADVERSE EVENTS

Report initiation for all AEs and serious adverse events (SAEs), (see [Section 9.3](#)), will begin at the time of the first treatment and continue up to the final study visit. All events will be followed to resolution or until 30 days after the subject completes the study. A final assessment of outcome will be made at that time.

All AEs must be recorded in the subject's medical records and on the CRF. AEs will be reported using customary medical terminology along with the following information: the onset and end dates, whether the event is considered to be a SAE (see [Section 9.3](#)), the impact the event had on study treatment (see [Section 0](#)), the CTCAE grade (intensity) of the event (see [Section 0](#)), the causality of the event (see [Section 0](#)), whether treatment was given as a result of the event (see [Section 0](#)), and the outcome of the event (see [Section 0](#)).

Impact on Study Treatment

The impact the event had on the study treatment will be assessed as either: dose increased, dose not changed, dose reduced, drug interrupted, drug withdrawn, unknown, and not applicable. The "not applicable" assessment will be used only when the subject is no longer in the treatment period of the protocol or died.

CTCAE Grade (Intensity) Assessment

The guidelines outlined in CTCAE v5.0 will be used for assessing the intensity of the event. The general guidelines for assessing the AE grade appear below. Full guidelines may be obtained at https://ctep.cancer.gov/protocolDevelopment/electronic_applications/docs/CTCAE_v5_Quick_Reference_5x7.pdf

Table 9-1: CTCAE v5.0 General Guidelines

Grade	Description
Grade 1	Mild; asymptomatic or mild symptoms; clinical or diagnostic observations only; intervention not indicated.
Grade 2	Moderate; minimal, local or noninvasive intervention indicated; limiting age-appropriate instrumental activities of daily living (ADL)*.
Grade 3	Severe or medically significant but not immediately life-threatening; hospitalization or prolongation of hospitalization indicated; disabling; limiting self care ADL†.
Grade 4	Life-threatening consequences; urgent intervention indicated.
Grade 5	Death related to AE.‡

*Instrumental ADL refer to preparing meals, shopping for groceries or clothes, using the telephone, managing money, etc.

†Self care ADL refer to bathing, dressing and undressing, feeding self, using the toilet, taking medications, and not bedridden.

‡Unlike the AE outcome assessment (see [Section 0](#)), a subject may have more than one Grade 5 event.

-Common Terminology Criteria for Adverse Events (CTCAE), v5.0: Nov 27, 2017

Causality Assessment

Adverse events will be assigned a relationship (causality) to the study treatment. The Investigator will be responsible for determining the relationship between an AE and the study treatment. The type of event, organ system affected, and timing of onset of the event will be factors in assessing the likelihood that an AE is related to the study treatment. Relationship of AEs to study treatment will be classified as follows:

- 1. Unrelated** – The event is definitely not associated with the study biologic or control. Other conditions including concurrent illness, progression or expression of the disease state, or reaction to a concurrent medication explain the reported AE.
- 2. Unlikely** – The temporal association, patient history and/or circumstances are such that the study biologic or control is not likely to have had an association with the observed event. Other conditions including concurrent illness, progression or expression of the disease state, or reaction to a concurrent medication, appear to explain the reported AE.
- 3. Possibly** – The event follows a reasonable temporal sequence from study biologic or control but could have been produced by the patient's clinical state or other therapies administered to the patient.

4. **Probably** – The event follows a reasonable temporal sequence from the study biologic or control, abates upon discontinuation of the study drug or control, or cannot be reasonably explained by known characteristics of the patient’s clinical state.
5. **Definitely** – The event follows a reasonable temporal sequence from the study biologic or control, abates upon discontinuation and cannot be explained by known characteristics of the patient’s clinical state.

Treatment Given as a Result of the Event

The event impact in terms of treatment provided will be as either: none, medication administered, non-drug therapy administered, surgery performed, hospitalization, or other (with a specification).

Outcome Assessment

The outcome of the event will be assessed as either: fatal, not recovered/not resolved, recovered/resolved, recovered/resolved with sequelae, recovering/resolving, and unknown. Only one AE per subject is allowed to have an outcome assessment as “death.” If there are multiple causes of death for a given subject, only the primary cause of death will have an outcome of death

Injection-site reactions

Injection-site reactions thought to be directly related to the injection are considered to be AEs of special interest, and will be assessed as per CTCAE v5.0.

For subjects who develop Grade 1 or Grade 2 events, therapy will be continued as per protocol. If a subject chooses to discontinue study treatment, the site should notify the protocol team leadership, and encourage the subject to complete any remaining study visits until the toxicity resolves.

For subjects who develop Grade 3 events following study drug injection, the subject should be reevaluated closely until the AE returns to Grade 1 or less, at which time study treatment may be reintroduced at the discretion of the site investigator. If the same Grade 3 AE recurs following the next administration of study drug, study treatment must be permanently discontinued. Subjects experiencing Grade 3 AEs requiring permanent discontinuation of study treatment should be followed closely for resolution of the AE to Grade 1 or less and the team leadership must be notified.

For Grade 4 events permanently discontinue therapy.

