6.4 INVESTIGATIONAL PRODUCT ADMINISTRATION

Guidelines for dose preparation can be found in the pharmacy manual.

Leronlimab (PRO 140) will be provided to the administering personnel in single-use syringes prepared from vials of study drug stored at 2-8°C at the site pharmacy prior to use. In Part 1 of the study, each of two syringes is filled to deliver 2.0 mL of study drug. Equivalent volumes of PRO 140 or placebo will be administered subcutaneously on opposite sides of the abdomen.

In Part 2 of the study, one syringe is filled to deliver 2.0 mL of study drug. Leronlimab (PRO 140) will be administered subcutaneously in the abdomen.

A 20-gauge needle should be used to remove PRO 140 or placebo from vial and a 25-gauge needle is used for administration to subjects.

Note: After the leronlimab or placebo solution is drawn into the syringe, it can be stored at

- room temperature (20°C to 25°C, 68°F to 77°F) for up to 2 hours, or
- refrigerated (2°C to 8°C, 36°F to 46°F) for up to 4 hours.

IP should be administered slowly over 15 seconds per mL.

Following each SC delivery of drug, careful examination will be made to assess the appearance of any study drug Injection Site Reactions (ISRs) as per CTCAE v5.0.

In Part 1 of the study, all doses of study drug will be prepared by either the unblinded credentialed pharmacist or qualified medical professional and will be provided to a blinded licensed healthcare professional at clinic site to be administered as SC injection. The blinding aspect is not applicable for the Part 2 of the study.

All Leronlimab (PRO 140) SC weekly injections must be administered at clinic by a healthcare professional.

Note: It is preferred that the same injection site be used throughout the study. At the same time, it is not recommended to inject the study drug into areas where skin shows signs of a previous injection site reaction. It is advised to change the injection site if any previous injection site reaction remains unresolved.

Post Injection Monitoring

Subject will be observed at approximately 30 minutes post-injection or longer, if necessary, for injection site reaction as per CTCAE v5.0.

In addition, the tolerability of repeated subcutaneous administration of PRO 140 is evaluated based on assessment of subject-perceived injection site pain using 11-point Numeric Pain Rating Scale.

Dose Modifications

The dose interruption, reduction, and permanent discontinuation for any toxicity are described below.

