Dose interruption: Refer to [Table 6-4](#) below. Recovery to acceptable levels must occur to allow Leronlimab (PRO 140) continuation.

Table 6-4: Leronlimab (PRO 140) Dose Modification and Management for Injection Site Reactions

CTCAE Grade	Treatment Modifications
Grade 1	No dose adjustment is required.
Grade 2	First Occurrence: No dose adjustment is required. Second Occurrence of the same event: Closely follow-up for resolution of the AE to Grade ≤ 1
Grade 3	Withhold treatment until symptoms resolve to: • Grade 1 or less
Grade 4	Study treatment will be permanently discontinued

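### Table 6-4 omits the stop that Section 9.2 requires when a Grade 3 injection-site reaction recurs, and Section 6.4 announces a dose reduction it never describes

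*Protocol*

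**What the plan says.** Three places in the protocol bear on a Grade 3 injection-site reaction.

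- **Section 6.4, Table 6-4.** The Grade 3 row reads "Withhold treatment until symptoms resolve to" Grade 1 or less. Only the Grade 2 row separates occurrences ("Second Occurrence of the same event: Closely follow-up for resolution of the AE to Grade" 1 or lower). Only the Grade 4 row ends in a stop: "Study treatment will be permanently discontinued". The line above the table adds: "Recovery to acceptable levels must occur to allow Leronlimab (PRO 140) continuation".
- **Section 9.2, Injection-site reactions.** After a first Grade 3 reaction the subject is re-evaluated until Grade 1 or less, "at which time study treatment may be reintroduced at the discretion of the site investigator". The text continues: "If the same Grade 3 AE recurs following the next administration of study drug, study treatment must be permanently discontinued".
- **Section 5.1.** Among the grounds on which an individual's treatment may be discontinued, in consultation with the Medical Monitor and the investigator, is a Grade 3 or higher event possibly or probably related to study drug.

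Section 6.4 introduces its dose-modification text with this promise: "The dose interruption, reduction, and permanent discontinuation for any toxicity are described below". What follows is one paragraph on dose interruption and Table 6-4, whose title limits it to injection-site reactions.

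**The concern.** Injection-site reactions are this protocol's adverse events of special interest. Clinic staff deciding whether to give the next weekly injection are likely to turn to the dose-modification table in the drug-administration section, and that table lacks the one mandatory stop the protocol sets for a repeated Grade 3 reaction. Because the Grade 2 row does distinguish first from second occurrence, a reader could reasonably take the undivided Grade 3 row to apply afresh each time: withhold, wait for recovery, resume.

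First, a stopping instruction could be missed for an individual subject. Second, whether that subject counts as an early termination, and so belongs to the per-protocol set, could depend on which page the site consulted. Separately, a reader of Section 6.4 is told that reduction rules and rules for other toxicities follow, and finds neither there.

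**Working it through.** This is mainly a comparison of texts; the plan states no figure to reproduce.

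**Step 1: set the provisions side by side.**

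| Event | Table 6-4 | Section 9.2 | Section 5.1 |
|---|---|---|---|
| First Grade 3 reaction | Withhold to Grade 1 or less | Re-evaluate to Grade 1 or less; resuming is at the investigator's discretion | May stop if related |
| Same Grade 3 reaction after the next dose | No separate instruction | Must stop permanently | May stop if related |
| Grade 3 reaction again after a later dose | No separate instruction | Not addressed | May stop if related |

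The second row is the main discrepancy: silence, a mandatory stop and a discretionary stop for one event. The third row is a gap, because the recurrence clause in Section 9.2 is tied to the next administration only. For Grade 4 reactions, Table 6-4 and Section 9.2 agree on permanent discontinuation.

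**Step 2: count the doses on which the readings could differ.** There are 13 weekly doses, T1 to T13 (Protocol Table 4-2). Assume each reaction resolves to Grade 1 or less before the next visit, so that no dose is withheld. This gives the upper bound.

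- First event at T1, recurrence at T2: T3 to T13 are at issue, 13 − 2 = 11 doses.
- First event at T2, recurrence at T3: T4 to T13 are at issue, 13 − 3 = 10 doses.

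If one dose is withheld after each event, the number falls. With a first event at T1, T2 withheld, recurrence at T3 and T4 withheld, T5 to T13 remain: 13 − 4 = 9 doses.

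**Step 3: follow the subject into the per-protocol set.** SAP Section 2.9.1 excludes subjects who miss two consecutive doses, fall below 80% compliance, or terminate before the 14-week evaluation. Counting a withheld dose as missed (the SAP does not say), compliance is doses given / 13:

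- one withheld: 12/13 = 92.3%
- two withheld: 11/13 = 84.6%
- three withheld: 10/13 = 76.9%, below 80%

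In the last scenario of Step 2, the table used alone gives doses T1, T3 and T5 to T13, which is 11/13 = 84.6% with no two consecutive misses. If no further dose is missed, the subject can stay in the set. Under Section 9.2 the subject stops after T3, with 2/13 = 15.4%, and is excluded both on compliance and as an early termination. So the same reactions can lead to different per-protocol membership.

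**Step 4: compare Section 6.4's announcement with its content.** Interruption is described. Permanent discontinuation appears only for Grade 4 injection-site reactions. No reduction is described there or elsewhere in the protocol or SAP. The words for a reduced dose occur only in the list of recording categories for an event's impact on treatment ("dose increased, dose not changed, dose reduced, drug interrupted, drug withdrawn"), which the SAP's adverse-event listings repeat.

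**The case against.** The strongest reply is that the table is incomplete, not contrary. It does not say to re-dose after every Grade 3 reaction, and Section 9.2 can be read as an added condition, so both can be obeyed at once. Section 11.4 obliges investigators to follow the whole protocol, and Section 5.1 still lets a site stop treatment. This reply largely stands. A reader might infer that the two sections state opposing rules and that sites would dose the same patient differently. The documents support only that a site using the table alone could do so.

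Numbers are also likely to be small. Section 1.6 describes most injection-site reactions as mild, and Section 5.5 halts the trial once three patients develop the same Grade 3 event attributed to study drug.

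Four other inferences are tempting, and the documents do not support them.

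- **A one-syringe reduction.** One of the two Part 1 syringes holds 2 mL × 175 mg/mL = 350 mg, the Part 2 dose, so a reader might fear an unregulated reduction. But Sections 4.2, 6.1 and 6.4 fix the Part 1 dose as two 2 mL injections, no reduced dose is defined, and Section 11.4 lists an incorrect dose as a major deviation.
- **A Grade 2 conflict.** Section 9.2 says therapy continues as the protocol provides, which can include Table 6-4. The table's second-occurrence entry asks for close follow-up, not withholding.
- **Recording categories as permission.** The options for a reduced or increased dose record what happened; they authorise nothing.
- **A distorted tolerability comparison.** SAP Section 9.3.7 handles tolerability with descriptive frequencies, listings and subject profiles. It specifies no formal test between doses, and the 350 mg arm is non-randomised and open-label.

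The complaint about other toxicities is also narrower than it looks. Section 5.1 does contain provisions for hypersensitivity, severe related events and liver injury; Section 6.4 simply does not point to them.

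**Conclusion.** The point holds as an omission with a practical consequence. Table 6-4 lacks the mandatory recurrence rule in Section 9.2, the two texts are not cross-referenced, and Section 5.1 adds a discretionary provision for the same event. Applied to a recurrence, the table's Grade 3 row alone permits a dose that Section 9.2 forbids.

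Per affected subject, the upper bounds are those of Step 2, 11 or 10 doses, and they assume that every reaction resolves before the next visit. How many subjects would be affected cannot be estimated, because neither document gives a rate of Grade 3 injection-site reactions for this population. The analysis consequence is confined to the per-protocol set, which is supportive only (SAP Section 7.2), and to descriptive summaries such as events leading to withdrawal. No effect on the primary comparison is shown.

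The mismatch in Section 6.4 is confirmed but does not by itself lead to different dosing. The case for acting is that a stopping instruction for individual subjects should be unambiguous wherever a site looks it up, and that the correction is nearly free.

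**What to change.** 1. Reconcile Section 5.1, Table 6-4 and the injection-site text of Section 9.2 so that all three state one rule for a first and for a recurrent Grade 3 injection-site reaction, including recurrence later than the next dose. The medical team decides what the rule is; this review takes no position.
2. Add cross-references between Table 6-4 and the injection-site text of Section 9.2, and from both to Section 5.1.
3. In Section 6.4, make the opening announcement match what the section contains: either remove the mention of reduction or describe what is meant, and refer to Section 5.1 for toxicities other than injection-site reactions.

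The cost is a protocol wording amendment and a memo to sites. It needs no new visits, procedures or subjects, and no change to the planned analyses.
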